### **Visit 4**

Subjects will return after the two weeks of treatment. They will return the completed sleep logs.

Subjective sleep symptoms will be evaluated using validated instruments including, Pittsburgh Sleep Quality Inventory (PSQI), and severity of insomnia - Insomnia Severity Index (ISI), and daytime sleepiness Epworth Sleepiness Scale (ESS), and daily visual analog scale (Karolinska sleepiness scale, KSS).

Objective sleep assessment will be performed using ambulatory 72 hour EEG, using sleep montage per standard AASM criteria, and scored by a registered polysomnography technologist using AASM guidelines. If the subject expresses hesitation because of the 72 hour EEG, then a 48 hour EEG will be offered.

Assessment of urine cortisol and catecholamines will be done as a measure of sympathetic function.

Subjects will continue to wear the actiwatch and complete sleep logs daily.

### **Visit 5**

Subjects will return for the EEG to be removed. They will return the Bioboosti, actiwatch and completed sleep logs.

The Bioboosti devices will be checked on their return to the study staff. If it is determined that the device is not functioning properly, the participant will be asked to redo the study.

Testing of each patient requires about one month as outlined above. With efficient recruitment and minimal attrition rate, 20 participants can complete the study.

### **Sustained Efficacy Phase**

Subjects participating in the study will also be asked if they are interested in the long-term use of BioBoosti device. In that case, they will be consented again to go forward with the long-term use. At the end of this process, they will be given sleep and headache logs.

They will be offered to continue the treatment for one year with regular follow-up. One month prior to each follow-up they will be asked to use the actiwatch to objectively evaluate the sleep patterns. They will either pick up the device or will be offered a home visit for the actiwatch use.

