### **Arm 1**

**Aim 1:** To test the hypothesis that treatment with BioBoosti has sustained efficacy in treating insomnia.

Our primary endpoint would be insomnia symptoms after 1 year of BioBoosti use as compared to initial symptoms (prior to starting treatment).

Measurement of insomnia will be done in serial comparisons every 3 months for ISI, TST (Total Sleep Time), WASO (Wake After Sleep Onset), as well as PSQI at year 1. We will use repeated measures ANOVA to compare ISI, TST, WASO, at months 3, 6, 9, and 12 and a T-test to compare PSQI at baseline to that after 1 year.

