We do not anticipate all 20 subjects to participate however, interested enrolled subjects will also be offered to continue the treatment for one year for the evaluation of sustained efficacy of BioBoosti as Insomnia Treatment. We *anticipate* enrolling up to 20 subjects at BWH and Faulkner Hospitals.

The study will also look at the effects of the BioBoosti device on sleep and recurrence of headache for patients who have been diagnosed with both insomnia and migraine. The study protocol remains the same besides the treatment with BioBoosti will be for 4 weeks to allow adequate headache assessment.

We anticipate enrolling 20 additional subjects with insomnia and comorbid migraine at Brigham and Women's and Faulkner Hospitals.

Briefly describe study procedures. Include any local site restrictions, for example, "Subjects enrolled at Partners will not participate in the pharmacokinetic portion of the study." Describe study endpoints.

The BWH and FH sleep clinics will be screened for follow-up patients with insomnia. Study staff will notify the treating physician to inform them of a potential subject. The treating physician will first introduce the study to the potential subject. If the subject gives permission and would like to obtain more information regarding the study, study staff will approach them and provide them with a copy of the consent form to review. Study staff may also contact the subject by phone to explain the study and recruit if it is more convenient for the subject. Study staff and a physician investigator will be available to answer all questions. If the potential subject is interested in participating in the study, the Principal Investigator will consult with the treating physician prior to enrolling the subject. If the subject decides to enroll in the study when approached in the clinic, we will proceed with Visit 1 (Enrollment Visit) that same day. The physician investigator will be available to speak with subjects during the consent process.

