### **Treatment phase**

There will be two weeks of treatment with Bioboosti. Subjects will be asked to use the device once a day, at approximately one hour prior to initiation of habitual sleep time. They will complete up to 6 therapy cycles. A therapy cycle consists of placing the Bioboosti on the Laogong point, which is located at the center of the palm. The device will remain there for 8 minutes, and this counts as 1 cycle. When the light on the device changes, it indicates that 8 minutes have passed, and a cycle is completed. The subject will then remove the device and replace it on the Laogong point of the other hand. The subject will repeat this up to 6 times, alternating the treatment cycles between one hand to another.

They will complete sleep logs for two weeks, as well as wear the actiwatch.

During this time, subjects should not drive while using the Bioboosti. They will also be advised to maintain a healthy lifestyle, as is done during clinic visits (light diet, regular exercise, smoking cessation, abstinence and sufficient sleep), but these are not terms of exclusion from the study.

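### The only endpoint named primary, insomnia at one year, is measured only in subjects who volunteer to go on, apparently after the two-week course, so the baseline-to-one-year comparison is at risk of selection toward benefit

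*Combined protocol and SAP*

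**What the plan says.** Under Arm 1, Aim 1 sets out to test sustained efficacy in insomnia and states: "Our primary endpoint would be insomnia symptoms after 1 year of BioBoosti use as compared to initial symptoms". No other endpoint in the document is called primary. The same paragraph plans a repeated measures ANOVA of ISI, TST and WASO over months 3, 6, 9 and 12, and a t-test of PSQI at baseline against one year.

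Research Design and Methods says who enters the year: "We do not anticipate all 20 subjects to participate however, interested enrolled subjects will also be offered to continue the treatment for one year". The Sustained Efficacy Phase section repeats that entry is by interest: "Subjects participating in the study will also be asked if they are interested in the long-term use of BioBoosti device". It adds: "In that case, they will be consented again to go forward with the long-term use". That section comes after Visit 5 of the insomnia schedule, where subjects hand the device back. The course before it is short: "There will be two weeks of treatment with Bioboosti".

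The plan sets no response criterion for entry and does not say when subjects are asked. It has no one-year follow-up of those who decline, no comparison of continuers with decliners, no definition of the analysis population and no method for missing data. Specific Aim 1 describes a within-subject, before-and-after design without a control group.

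**The concern.** A subject who felt no better after two weeks has less reason to take on a year of nightly sessions than one who slept well. If uptake follows that logic, the one-year group is chosen partly on an early reading of the outcome it will later be judged on, and is then compared with its own pre-treatment score. Natural fluctuation or expectation that looked like improvement at Visit 4 would carry into the one-year comparison to the extent that the two changes are correlated. With no control arm, nothing offsets it. An ineffective device could then appear to show sustained efficacy, and readers would apply the result to insomnia patients generally.

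**Working it through.** The plan gives no power calculation, significance level, expected uptake or correlation, so it has no figure of its own to reproduce. The check asks how large the distortion could be.

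**Inputs from the plan.** 20 subjects in the short course; fewer than 20 expected to continue; a paired t-test of baseline against one year (PSQI).

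**Assumptions.** True mean change is zero at both times. Changes are normal with SD 1. The correlation r between Visit 4 change and one-year change is 0.3, 0.5 or 0.7. The test is two-sided at 5%, counting only significant results in the device's favour (nominal 2.5%).

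**Shift in the mean.** If the best k of 20 on Visit 4 change continue, and their mean Visit 4 change is m(k), the expected spurious one-year change is

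shift = r × m(k).

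- k = 10: m = 0.77 (simulated). Shift = 0.3 × 0.77 = 0.23, 0.5 × 0.77 = 0.38, 0.7 × 0.77 = 0.54 SD.
- k = 15: simulated shifts are 0.12, 0.20 and 0.28 SD.

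For partial selection, the choice depends on Visit 4 change plus independent noise of equal variance. The shift is then divided by √2. For k = 10 this gives 0.23/1.41 = 0.16, 0.38/1.41 = 0.27 and 0.54/1.41 = 0.38 SD.

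**Chance of a significant improvement when there is none (simulated).**

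| How subjects choose | Continue | r = 0.3 | r = 0.5 | r = 0.7 |
|---|---|---|---|---|
| Unrelated to response | any number | 2.5% | 2.5% | 2.5% |
| Partly on response | 18 of 20 | 4% | 5% | 6% |
| Partly on response | 15 of 20 | 5% | 8% | 12% |
| Partly on response | 10 of 20 | 7% | 13% | 22% |
| Exactly the best | 15 of 20 | 7% | 13% | 23% |
| Exactly the best | 10 of 20 | 10% | 22% | 45% |

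A milder choice model (logistic, slope 1 per SD of Visit 4 change) gives 5%, 8% and 13% for 10 of 20. If r = 0, the rate is 2.5% whatever drives the choice.

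**Which analysis this applies to.** The calculation models a paired test against baseline, which the plan specifies only for PSQI. The ANOVA of ISI, TST and WASO lists months 3 to 12 without baseline. As written it does not test the endpoint as defined, and selection need not favour benefit there.

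**The case against.** The strongest reply is that the plan does not say what a suspicious reader might infer from it.

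- **Self-selected responders.** A reader might infer that the year is entered only by people who improved, so that the endpoint is biased as a matter of fact. The documents do not support that. Entry rests on interest, with no response criterion. The time of asking is only implied, by the section's place after Visit 5 and by the idea of continuing. A separate payment of $350 gives a motive unrelated to response. That motive dilutes selection but does not remove it unless it makes uptake independent of response.
- **The migraine arm.** A reader might extend the point to subjects coming off the one-month course. The primary endpoint belongs to Arm 1, and the one-year phase sits in the insomnia schedule. The migraine schedule ends at Visit 6 with no such phase. The headache logs mentioned under the Sustained Efficacy Phase leave access for that arm unclear at most.
- **Decliners as treatment failures.** Every insomnia subject returns the device at Visit 5 by protocol. A decliner has completed the planned course, and sustained use was never observed in that person. Their Visit 4 data still serve Hypothesis 1.
- **The endpoint presupposes use.** It is defined after a year of use, so a comparison in continuers is what it literally describes. This stands, and it makes the problem largely one of how far the result generalises.
- **The size.** The 10 to 45% range needs half to continue and these to be exactly the best ten. With high uptake and partial selection the inflation is small.

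What remains is that nothing in the plan prevents, measures or reports the selection.

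**Conclusion.** The concern holds as a risk of bias, not as a demonstrated one. The sole primary endpoint will be observed only in insomnia-arm subjects who opt in and consent again, the opt-in appears to follow the two-week course, and those who decline are not handled. The comparison with baseline is therefore exposed to selection, most plausibly toward benefit. Against a nominal 2.5%, the chance of a false improvement runs from no inflation, through 4 to 12% with 15 to 18 of 20 continuing under partial selection, to 10 to 45% in the extreme case. The position within that range depends on uptake and on the correlation between early and one-year change, and the documents give neither.

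This should be fixed, because Aim 1 is framed as a test of sustained efficacy. It does not invalidate a study that calls itself a pilot. Regression to the mean and expectation would remain even if all 20 continued, because there is no control group.

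**What to change.** In the Sustained Efficacy Phase section:

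1. Ask for and record the one-year decision before the short-course outcome is known: at Visit 1, and no later than device hand-over at Visit 3. Define the one-year group as those who agreed then.
2. Seek month-12 ISI and PSQI, by telephone if needed, from members of that group who later stop using the device. Report the comparison that includes them as a supporting analysis beside the Arm 1 endpoint, which is defined after a year of use.
3. Report uptake, and tabulate baseline and Visit 4 ISI and PSQI for continuers and non-continuers. The insomnia schedule already collects these scores at Visits 2 and 4, so this also works for subjects already past Visit 4.
4. Word the one-year conclusion as applying to subjects who chose to continue.

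The cost is a small amendment to consent timing, a few telephone questionnaires and one table. Some who agree early will stop, so the reported one-year effect may be smaller and the claim will be narrower. The change addresses selection only; it does not supply a control.

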### For Insomnia

#### **Visit 1**

Subjects who are interested in participating will sign the consent form. A screening physical exam will be done, and vital signs (blood pressure, heart rate, pulse rate, respiratory rate) will be measured. Pregnancy test will be done for women of childbearing potential.

Subjects will go home with sleep logs, which are subject records of when they go to sleep and wake up. They will also be given an actiwatch to wear, as an objective measure of sleep and wake periods.

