#### **Visit 2**

Subjects will be scheduled for a follow up at FH.

Subjective sleep symptoms will be evaluated using validated instruments, including Pittsburgh Sleep Quality Inventory (PSQI), and severity of insomnia - Insomnia Severity Index (ISI), and daytime sleepiness Epworth Sleepiness Scale (ESS), and daily visual analog scale (Karolinska sleepiness scale, KSS).

Objective sleep assessment will be performed using ambulatory 72 hour EEG, using sleep montage per standard AASM criteria, and scored by a registered polysomnography technologist using AASM guidelines. If the subject expresses hesitation because of the 72 hour EEG, then a 48 hour EEG will be offered.

Assessment of sympathetic autonomic nervous system function will be done by measuring cortisol and catecholamine levels using standard assays.

Subjects will continue to wear the actiwatch and complete sleep logs daily.

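### The 1-year analysis of TST and WASO names neither the measuring instrument nor a baseline time point, so the change from pre-treatment is untested as written and, if an EEG baseline is added, confounded with instrument

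*Combined protocol and SAP*

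**What the plan says.** **Endpoint and tests (Specific Aims, Arm 1).** The endpoint is a comparison with pre-treatment status: "Our primary endpoint would be insomnia symptoms after 1 year of BioBoosti use as compared to initial symptoms (prior to starting treatment". The measures follow: "Measurement of insomnia will be done in serial comparisons every 3 months for ISI, TST (Total Sleep Time), WASO (Wake After Sleep Onset", with PSQI at year 1. The test for the serial measures is: "We will use repeated measures ANOVA to compare ISI, TST, WASO, at months 3, 6, 9, and 12". Baseline is named only for the questionnaire: "a T-test to compare PSQI at baseline to that after 1 year".

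**Instruments before treatment (For Insomnia).** At Visit 1: "They will also be given an actiwatch to wear, as an objective measure of sleep and wake periods". At Visit 2: "Objective sleep assessment will be performed using ambulatory 72 hour EEG", with a 48-hour recording as the fallback. The actiwatch stays on during this period and sleep logs are kept.

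**Instruments in the 1-year phase (Sustained Efficacy Phase).** "One month prior to each follow-up they will be asked to use the actiwatch to objectively evaluate the sleep patterns". The month 3, 6, 9 and 12 visits list actiwatch return, sleep logs and questionnaires. None lists an EEG.

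No section states whether TST and WASO come from EEG, actiwatch or sleep logs at any time point.

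**The concern.** The endpoint needs a pre-treatment TST and WASO, and the stated test does not include one. Whoever runs the analysis will have to add it, and two objective candidates exist. The Visit 2 text describes the EEG as the means of assessing sleep objectively, so it is a plausible choice. At month 12, however, only the actiwatch (or the log) is available.

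EEG-scored sleep and a movement-based estimate are different measurements, taken over different windows: two or three nights against roughly a month. In a single-group before-after design, a constant gap between them cannot be separated from a treatment effect. It could create an apparent benefit or hide a real one, depending on its sign. Leaving the source open also allows the choice to be made after the data are seen.

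**Working it through.** The plan gives no alpha, SD, effect size or sample-size derivation, so there is no figure of its own to reproduce.

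**Step 1: sources by time point**

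| | Before treatment | Months 3, 6, 9, 12 |
|---|---|---|
| EEG | yes (Visit 2) | none listed |
| Actiwatch | yes (from Visit 1) | yes |
| Sleep logs | yes | yes |
| In the stated ANOVA | no | yes |

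**Step 2: what each contrast estimates.** Let τ be the true change at month 12 and g the mean actiwatch-minus-EEG gap on the same sleep.

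- Month 12 actiwatch minus baseline actiwatch has expectation τ. A constant gap cancels.
- Month 12 actiwatch minus baseline EEG has expectation τ + g.
- Contrasts among months 3, 6, 9 and 12 contain no g. If the effect is fully present by month 3 and then holds, they contain no τ either. Sustained benefit and no benefit at all therefore look the same to the ANOVA as listed.

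**Step 3: illustration of the second contrast with τ = 0.** Assumptions not in the documents: two-sided alpha 0.05; offset δ = g / (SD of the paired difference) between 0.25 and 1; n = 10 and n = 20. Research Design and Methods expects fewer than all 20 to continue, so 20 is the upper end.

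For a paired t-test, with critical value c = t(0.975, n−1) and noncentrality λ = δ√n:

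false-positive rate = 1 − F(c; n−1, λ) + F(−c; n−1, λ), where F is the noncentral t distribution function.

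- n = 20, δ = 0.5: λ = 0.5 × √20 = 2.24, rate 0.565.
- n = 10, δ = 0.5: λ = 0.5 × √10 = 1.58, rate 0.293.

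The plan assigns an ANOVA to TST and WASO, so that was also simulated: 10,000 runs, compound symmetry, no true effect, and the offset added to the four follow-ups in units of the paired-difference SD.

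| Offset δ | Paired t, n=20 | ANOVA with EEG baseline, n=20 | Paired t, n=10 | ANOVA with EEG baseline, n=10 |
|---|---|---|---|---|
| 0.25 | 0.19 | 0.16 | 0.11 | 0.10 |
| 0.5 | 0.57 | 0.57 | 0.29 | 0.28 |
| 0.75 | 0.89 | 0.92 | 0.56 | 0.60 |
| 1.0 | 0.99 | 1.00 | 0.80 | 0.87 |

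With months 3 to 12 only, as the plan lists them, the simulated rejection rate stayed between 0.045 and 0.053 at every offset. With actiwatch at baseline as well, a constant offset cancels and the rate is the nominal 0.05.

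**The case against.** A reader might infer that the planned 1-year test already sets an EEG baseline against actiwatch follow-up, so that its error rate is inflated by design. The documents do not support that.

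- The ANOVA lists only months 3, 6, 9 and 12, all measured within the actiwatch phase. As written it mixes nothing and holds its level.
- No text assigns TST or WASO to EEG. The actiwatch is described as an objective measure both before treatment and in the 1-year phase, so a like-for-like reading is at least as natural.
- The change of instrument is not forced, because pre-treatment actiwatch data are already collected.
- Sleep logs run through both phases, and the plan does not say that TST and WASO must be objective.
- ISI and PSQI use the same instrument throughout, so no instrument gap touches them.

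All of this stands, and it limits the point to TST and WASO and to specification. It does not remove the point. The first item shows that the stated test does not answer the stated question. Once baseline is added to answer it, the choice of instrument matters and nothing in the plan settles it.

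**Conclusion.** The point holds as a specification gap with two linked parts: the ANOVA omits the baseline that the endpoint requires, and the source of TST and WASO is never named. The first part is certain from the text. The second becomes a bias only if an EEG value is used as baseline, which is possible but not stated.

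The size of that bias cannot be determined from the documents, which give neither an EEG-actiwatch gap nor an SD. The rates of about 57% (n=20) and 29% (n=10) at an offset of half an SD are conditional on an EEG baseline, no true effect and the assumed alpha. They show how sensitive the comparison would be and do not predict what will occur. The gap deserves correction before analysis because it affects measures listed under the 1-year endpoint in a study with no control group.

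**What to change.** In Specific Aims, Arm 1:

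1. Add baseline to the repeated measures model, and state that the contrast of interest is month 12 against baseline.
2. Define TST and WASO for the 1-year analysis as actiwatch values scored with the same algorithm at baseline and at months 3, 6, 9 and 12. Baseline is the Visit 1 to Visit 2 nights, before the EEG and before the device.
3. Restrict EEG values to the short before-after contrast.
4. Report the number of nights averaged at each time point.

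The cost is a few sentences, with no new visits, data or burden on participants. There is one small drawback. The insomnia schedule gives no interval between Visits 1 and 2, and Visit 5 puts the whole sequence at about one month. Taking 30 days, less 14 of treatment and two EEG recordings of 2 to 3 days each, leaves roughly 10 to 12 nights. The baseline mean will therefore probably rest on fewer nights than the follow-up means and be less precise, which is why the night counts should be reported.

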### **Visit at 3rd, 6th, 9th months**

- Subjects will complete the Insomnia Severity Index (ISI) and Pittsburgh Sleep Quality Inventory (PSQI).
- They will return the completed sleep logs.
- They will be asked to continue filling out new sleep logs for the following visit.
- They will return the Actiwatch.

## **Visit at 12th month**

Subjects will be asked to return the sleep logs and actiwatch and will be asked to complete the Pittsburgh Sleep Quality Inventory (PSQI), and Insomnia Severity Index (ISI), and daytime sleepiness Epworth Sleepiness Scale (ESS).

## **For Patients with Insomnia and Migraine**

We do not anticipate for this longer testing period to increase the risk, as to date, none of the individuals with insomnia have reported any negative effects from the treatment.

